Three-dimensional digital breast tomosynthesis (DBT) is a new screening tool, which is argued to be better than standard digital mammography (DM) (7-17). The statement is based on a lower recall rate (call-back for further examination after abnormal findings on the screening mammograms) and a higher rate of screen-detected cancer. The basis for the statement is three prospective studies (7-9) and eight retrospective (10-17). However, all the retrospective studies are performed in the U.S. where the screening differ substantially from how it is performed in Norway and Europe (18, 19). In addition, the statement is based on results from two vendors only, Hologic and Siemens.

2. Aspects related to the research project

Background and status of knowledge: DM is the most commonly used screening tool to detect breast cancer in Europe today (20). DM was fully implemented in the Norwegian screening program in 2011. However, the sensitivity of DM is as low as 50% for women with mammographic dense breasts (21) and studies have shown 4-5 times higher risk of breast cancer in women with dense versus fatty breast (22). Whether women with dense breast should be screened with other technologies as DM is thus discussed.

DBT has potential to reduce the effect of tissue superimposition and capable to improve the sensitivity of the interpretation for some examinations. The technology is often used adjacent to DM. Some vendors offer synthetic two-dimensional DM generated from the DBT data (2D) and studies have shown similar detection rate as of additional standard DM (23-25). A systematic review from 2013 concluded that two-view DBT had equal or better accuracy compared with two-view DM, while one-

view DBT did not have better accuracy than two-view DM (26). The review highlighted the urgent need for large screening studies of this technology to complement the available evidence.

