Studies on performance measures: *Prospective studies:* The STORM-trial in Italy (8), the Oslo trial in Norway (7), and the Malmo-trial from Sweden (9) compared performance measures (i.e. recall rate, cancer detection, positive predictive value, tumor characteristics) within women screened with DM and DBT with DM or 2D. The STORM trial compared the outcome of sequential screen-readings; the same radiologists read DM first, and thereafter DBT. A significant higher rate of screen-detected cancer, 2.7/1000 and a lower recall rate was found for DM+DBT compared with DM. The Oslo trial assigned the radiologists to read DM or DM+DBT. They found an increase of 1.9 cancers/1000 screens using DM or 2D+DBT. The additional cancers were mostly invasive cancers. The recall rate decreased. The Malmo-trial compared the outcome of two-view DM with one view DBT. A significant increase of 2.6 cancers/1000 screened for one-view DBT was observed. The recall rate increased. The majority (17 of 21) of the cancers were invasive. *Retrospective studies:* Results from eight retrospective studies of DBT adjunct to DM are available of today (10-17). All the studies are conducted in the U.S. where the screening protocol differ substantially from the one used in Norway and Europe (18). Two of the studies (12, 13) compared performance measures before and after the introduction of DBT, while Haas et al. (10) compared the outcome of DM versus DM+DBT within the same timeframe. A clear trend toward a higher rate of screen-detected cancer and a reduction in recall rate were observed in all the studies.

Economic studies: Only two studies, both from the U.S. have considered the costs of DBT (27, 28). One of the studies concluded that DM+DBT resulted in cost savings compared with standard DM in a simulated screening cohort, mainly due to fewer recalls and earlier diagnosis, while the other study found that DM+DBT might be cost-effective for women with dense breasts.

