Study II: *Use of tomo versus DM in a population based screening program – a randomized controlled trial.* This study deal with the epidemiologic and radiologic aspects of the project.

How do the recall rates, including false positive screening results differ between the groups? How do the rates of screen-detected DCIS and invasive breast cancer differ? How do the PPV-1 and PPV-2 differ between the two groups? How do the mammographic features in screen-detected cancers differ between the two groups? The results will include results from the entire study period. The number of women and cases will be approximately twice as much as Study I. The same statistical approach as in Study I will be used.

Study III: *Prognostic and predictive histopathologic characteristics of breast tumors detected in a population based screening program using tomo versus DM.* This study focuses on prognostic and predictive histopathologic characteristics of the tumors.

How do the prognostic characteristics (morphology, tumor size, histologic grade and lymph node involvement) differ between the two groups? What about stage distribution? How do the predictive characteristics (estrogen (ER) and progesterone (PR) receptor status, Her2Neu and Ki67) differ? What about subtypes based on immunohistochemical analyses and Nottingham Prognostic Index?

Low stage Luminal A-like tumors might indicate low progression compared with late stage Her2+ or TN tumors. Differences in distributions of the characteristics, and thus different treatment algorithm between the tomo and DM groups might indicate whether the tumors detected with tomo represent low progression compared with those detected with standard DM. Descriptive analyses will compare rates and percentages. Logistic regression analyses will be used to estimate the odds of having breast cancer with specific characteristics diagnosed (37).

Study IV: Tomo and DM in a population based screening program – which technology has the highest sensitivity for women with mammographic dense breast? We will stratify analyses on early performance measure of tomo versus DM by density, using Volpara® density measure.

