How do the early performance measures given in study II+III differ by mammographic density? Volpara® is installed at the screening units at Danmarksplass and data is available for this study. We will use descriptive analyses to compare distributions and rates, while logistic regression analyses will be performed to estimate the odds ratio of recalls and breast cancer (37).

Studies V and VI: Costs of tomo and DM in a population based screening program – Is tomo cost-effective? Study V will deal with early costs related to time spent at screening and reading, the recall rates, diagnostic procedures, treatment and total costs for the two techniques. Data from the first year of the trial will be used. A previous study from Norway, which showed that treatment costs are highest during the first year following a diagnosis will serve as a methodological basis for the analysis (38). Using a similar approach, we will compare treatment costs for interval cancers, recurrence and early costs of cancers detected in the following screening round, using the full two year follow-up in Study VI. Results will be presented as cost per recurrence, interval and subsequent breast cancer avoided. Possible differences between groups in these outcomes should be well captured during the two years. Mortality may also be used as an additional outcome in the cost-effectiveness analysis in If the project is sufficient funded, study VI, although the follow-up time is too short, will use a simulation model with mortality estimates from the Cancer Registry. Additional cost estimates for the period beyond two years will be run (33) as inputs can be run to estimate the cost-effectiveness in the life-long perspective for the women (as e.g. in (28)). A major advantage of Studies V and VI compared with the U.S. studies (24, 25), is the availability of individual level data within the project, thus avoiding most assumptions of recall rates, cancer stage distributions, diagnostic and treatment costs etc. from earlier studies. This ensures a higher level of detail when defining the list of cost components, and more precise estimates of the variation across patients in both effect outcomes and costs.

A prospective cohort study: We will perform a prospective cohort study. During the study period, about 45,000 women will be invited to screening at Danmarksplass and 35,000 (75%) are expected to participate (Table 1).

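### Study IV asks about sensitivity in dense breasts, but no planned analysis combines screen-detected and interval cancers by density

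*Combined protocol and SAP*

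**What the plan says.** The title of Study IV (section 2) poses the question "which technology has the highest sensitivity for women with mammographic dense breast". The analysis under it is narrower: "We will stratify analyses on early performance measure of tomo versus DM by density, using Volpara® density measure". The operative question that follows is "How do the early performance measures given in study II+III differ by mammographic density".

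The Study II measures are recalls and false positives, screen-detected DCIS and invasive cancer, PPV-1, PPV-2 and mammographic features. Study III adds tumour characteristics. Study IV also plans logistic regression for recalls and breast cancer.

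Interval cancers appear elsewhere:
- Table 1 expects 2.0 per 1000, or 35 per arm.
- Section 3 plans follow-up for two years after the screening exam, including cancers in the next round.
- Study VI uses them for costs: "we will compare treatment costs for interval cancers, recurrence and early costs of cancers detected in the following screening round".
- Table 2 schedules an analysis of interval and subsequent cancers (rates, histopathology, mammographic features) for January to December 2020.

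Table 2 places paper IV in October 2018 to March 2019. The trial screens women until December 2017, so two-year follow-up is complete only in December 2019.

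**The concern.** Screening sensitivity is the share of all cancers present that the screen finds. Its denominator needs the missed cancers, which in a screening programme are counted mainly as interval cancers. Study IV's measures contain the numerator only. The later work with interval cancers names neither a density split nor a sensitivity. Overall sensitivity by arm could be assembled from Study II and the 2020 rates; the density-specific version, which is what Study IV asks for, could not.

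The Background motivates the dense-breast question by stating that "the sensitivity of DM is as low as 50% for women with mammographic dense breasts". A reader of paper IV will expect an answer in the same terms. If paper IV finds more cancers with tomo in dense breasts, the title invites that result to be reported as higher sensitivity. Extra screen-detected cancers may be averted interval cancers, cancers brought forward from the next round, or over-diagnosed cancers. Detection by density does not separate these. Study III bears on over-diagnosis only indirectly, through characteristics that "might indicate whether the tumors detected with tomo represent low progression compared with those detected with standard DM".

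**Working it through.** **Inputs.** Table 1, per arm: 17,500 participants, 6.0 per 1000 screen-detected, 2.0 per 1000 interval cancers. From section 2, Studies on performance measures, for the Oslo trial: "They found an increase of 1.9 cancers/1000 screens using DM or 2D+DBT". The share of women with dense breasts and their relative risk are not in the documents in usable form (the Background gives 4-5 times for dense versus fatty only), so they are assumed below.

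**1. The plan's own figures.** 17,500 × 6.0/1000 = 105 and 17,500 × 2.0/1000 = 35, as in Table 1. The plan states no sensitivity. Taking Table 1's interval cancers as those within two years, sensitivity = screen-detected/(screen-detected + interval) = 105/140 = 75%, over all densities.

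**2. Detection ratio against sensitivity ratio.** An increase of 1.9 per 1000 on 17,500 women is about 33 cancers. The detection ratio is (6.0 + 1.9)/6.0 = 1.32. Suppose none of the 33 is over-diagnosed and all are brought forward from the next screen, so interval cancers stay at 35:
- sensitivity = (105 + 33)/(105 + 33 + 35) = 138/173 = 80%
- sensitivity ratio = 79.8/75 = 1.06

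If all 33 were over-diagnosed instead, the arithmetic would be the same. Even the rise from 75% to 80% reflects no fall in interval cancers, so two-year sensitivity also needs the interval-cancer and next-round rates beside it.

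**3. The same detection with different interval cancers.** At the 0.25-point increase in the power statement (8.5 per 1000, about 149 cancers), sensitivity is 149/(149 + 35) = 81% if interval cancers are unchanged, and 149/(149 + 20) = 88% if they fall to 20. Detection alone does not fix sensitivity.

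**4. Timing.** Assume even enrolment over January 2016 to December 2017, interval cancers spread evenly over 24 months, and no registration delay.
- 1 October 2018 (month 33): 9/24 of women have full follow-up; the other 15/24 average 16.5 of 24 months. Fraction accrued = 0.375 + 0.625 × 0.6875 = 0.805, or 28.2 of 35. Apparent sensitivity = 105/133.2 = 79%.
- 31 March 2019 (month 39): 15/24 complete; the other 9/24 average 19.5 of 24 months. Fraction = 0.625 + 0.375 × 0.8125 = 0.930, or 32.5 of 35. Apparent sensitivity = 105/137.5 = 76%.

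Timing alone moves the figure by 4 points or fewer. The missing analysis is the main issue.

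**5. Precision in dense women.** With an assumed dense share s and risk r relative to all other women, cancers per arm N = 140sr/(sr + 1 − s). The 95% CI half-width for the difference in sensitivity is 1.96 × √(2p(1 − p)/N), with p the same in both arms.

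| s | r | N | half-width, p = 75% | half-width, p = 50% |
|---|---|---|---|---|
| 20% | 1 | 28 | 23 points | 26 points |
| 30% | 2 | 65 | 15 points | 17 points |

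**The case against.** **Only the title is wrong.** Study IV's operative question already asks about early measures by density, and section 2 (Gaps of knowledge) says openly that waiting years for interval cancers before stating an effect is not acceptable. Early measures first is a declared choice. This stands, and it is why rewording deals with most of paper IV's problem. It does not supply the sensitivity that the title promises.

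**The analysis may already be covered.** The regression for recalls and breast cancer is not expressly limited to screen-detected cancer, and section 3 says that all studies except I and V share one dataset. But the regression sits under a question confined to Study II and III measures, and the odds of having cancer are not sensitivity. Having the data is not a planned analysis.

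**Randomisation makes the detection ratio a fair proxy.** With comparable arms it may indicate relative sensitivity, but excluding over-diagnosis is not enough: the 1.32 against 1.06 example contains none.

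**The added table cannot settle the question.** At half-widths of 15 to 26 points it will rarely do so. That is a reason to show intervals, not to let detection stand in.

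Stronger readings are tempting but unsupported:
- A reader might infer that the plan ignores interval cancers. It follows them up and analyses them; only the density split and the combination are missing.
- A reader might apply the increases from earlier studies (for one-view DBT, "A significant increase of 2.6 cancers/1000 screened for one-view DBT was observed") to Table 1 and obtain tomo sensitivities near or above 100%. Those are absolute increases from other settings whose baseline rates the documents do not give, and they are not by density. The 1.9 per 1000 above serves only as an illustration.
- A reader might infer that density readings differ between arms because the images differ. The documents do not say which images the density tool reads, so this is an open assumption, not a shown fault.
- Section 4 links higher sensitivity to greater programme effectiveness. That is a general remark and does not rest on Study IV.

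**Conclusion.** The gap is real and limited. As written, the plan does not deliver density-specific sensitivity, so Study IV cannot answer its title question, and higher detection in dense breasts could be reported as higher sensitivity. On Table 1's figures the two can be as far apart as 1.32 and 1.06. That example assumes an increase of 1.9 per 1000, all of it brought forward or over-diagnosed, over all densities; the size within dense breasts cannot be worked out from the documents. The precision figures rest on an assumed dense share of 20-30% and a relative risk of 1-2. The trial's randomised comparison, data collection and other studies are unaffected. The change should be made before paper IV is analysed.

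**What to change.** 1. Word paper IV's question and conclusions as detection, recall, PPV and tumour characteristics by density. State that detection ratios are not read as relative sensitivity, because extra cancers may be over-diagnosed or brought forward from the next round rather than averted interval cancers.
2. Add to the 2020 analysis, by arm and density with 95% CIs, the interval-cancer rate and sensitivity = screen-detected/(screen-detected + interval cancers within two years). Show both beside next-round cancer rates, since over-diagnosis and lead time each inflate this sensitivity.
3. State, for every density-stratified comparison and not only for sensitivity, the assumption that density is measured comparably in both arms.

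The cost is wording for paper IV and one added table in 2020. Density is already part of the screening data, and interval and next-round cancers are already followed up. The downside is that the sensitivity result comes about a year after paper IV and will be imprecise in dense women.

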Table 1: Number of women in the target group of the Norwegian Breast Cancer Screening Program, Hordaland - Danmarksplass, estimated number of participants, recalled women and breast cancer cases in the planned project

[figure not shown]
	Total	Control group DM	Study group Tomo (Synthetic DM+DBT)
Target group (n)	45 000	22 500	22 500
Expected participants *	37 500	17 500	17 500
Expected recalls*	3%	525	525
Expected screen-detected cancers* [∞]	6.0/1000	105	105
Intervalcancer*	2.0/1000	35	35

*Based on numbers from 2013 and 2014; [∞]Screen-detected ductal carcinoma in situ (DCIS) and invasive breast cancer

Randomization: The women targeted our study will be invited to the Norwegian Breast Cancer Screening Program, at Danmarkspllass, as usual. The women are residing in rural and urban areas in Hordaland county. All attending women will be asked if they are willing to participate in the study after they have received written and oral information about the study from the radiographers. Those who accept the invitation will sign an informed consent that the radiographers will be responsible to collect, before they are randomized into tomo (intervention group) or DM (control group). Experiences from the Oslo Tomosynthesis Trial shows that about 98% of the women who were asked, agreed to take part in the study. About 70% of the attending women were asked. Those who do not agree to participate in the planned study will be screened with DM. Their data will not be included in our study.

Power estimations: Using the populations given in Table 1 indicate that the difference between DM and tomo have to be 0.25% or more to be statistically significant different in the two groups, given a power of 0.8 and a p-value of 0.05 (Figure 1).

Figure 1: Estimated power for a two-sample proportion test for the

expected number of women included in the study

Screen-reading: Seven breast radiologists will be involved in the reading. Results from the Oslo Tomosynthesis Trial showed that reading tomo required 30 seconds more/each exam compared with DM. A reading schedule will ensure that all radiologists read the same number of tomo and DM. All screening exams, regardless of technology used, will have the same independent double reading as the usual procedures in the screening program.

3. The project plan, project management, organisation and cooperation

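### Study IV asks how the tomo-versus-DM measures differ by breast density, but no technology-by-density interaction is specified to answer that question

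*Combined protocol and SAP*

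**What the plan says.** The protocol (section 2, Study IV) contains two different questions. The title asks "which technology has the highest sensitivity for women with mammographic dense breast", which concerns one stratum. The question below it is "How do the early performance measures given in study II+III differ by mammographic density", which concerns how a between-arm contrast changes across strata.

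The method is given in two places. The first is "We will stratify analyses on early performance measure of tomo versus DM by density"; density is to be measured with Volpara. The second adds descriptive comparison of distributions and rates, and says that "logistic regression analyses will be performed to estimate the odds ratio of recalls and breast cancer (37").

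The protocol does not give the number of density strata, the cut-points, an interaction term or a heterogeneity test. The only power statement (section 2, Power estimations) is for the whole sample: "the difference between DM and tomo have to be 0.25% or more to be statistically significant different in the two groups". It assumes 80% power and a 5% significance level.

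Table 2 schedules paper IV for October 2018 to March 2019. The analysis of interval and subsequent cancers is scheduled for January to December 2020.

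**The concern.** The measures of Studies II and III are comparisons of tomo with DM. To ask how they vary with density is to ask whether the technology effect differs between women with dense and non-dense breasts. Separate stratum results do not answer that. One stratum can pass 0.05 and the other miss it when the two effects are the same, because each stratum has only part of the sample.

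The background section says that screening women with dense breasts by other technologies is under discussion, and section 5 places paper IV in the field of risk-stratified screening. A density-specific reading of the results is therefore likely, and the plan has no direct estimate of the difference in effect to set against it.

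**Working it through.** **Inputs from the protocol.** Table 1: 17,500 women per arm and 6.0 screen-detected cancers per 1000. Power estimations: a difference of 0.25 percentage points, power 0.8, alpha 0.05 (taken as two-sided). The description of the prospective studies: an increase of 1.9 per 1000 in the Oslo trial.

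**Assumptions.** The protocol gives no density shares and no detection rates by density. I take two strata, a dense share s of 30-50%, and a DM detection ratio r (dense/non-dense) of 1 to 2.

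**Step 1: the plan's own figure.** For a two-proportion z test with pooled variance:

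power = Φ[(d − 1.96·SE0)/SE1], with SE0 = √(2p̄(1−p̄)/n) and SE1 = √(p0(1−p0)/n + p1(1−p1)/n).

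With p0 = 0.0060, p1 = 0.0085 and n = 17,500: SE0 ≈ SE1 ≈ 0.000907, so power = Φ[(0.0025 − 0.00178)/0.000907] = 0.787. The difference detectable with 80% power is 0.254 points. Table 1's total of 37,500 would mean 18,750 per arm, which gives power 0.814 and 0.245 points. The stated 0.25 reproduces for cancer detection.

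**Step 2: the common effect.** OR = (0.0085/0.9915)/(0.0060/0.9940) = 1.42, applied in both strata.

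**Step 3: stratum rates and power.** The non-dense DM rate is f = 0.006/(s·r + 1 − s) and the dense DM rate is r·f. Step 1 is repeated with n·s and n·(1−s) per arm. For s = 0.5 and r = 1, each stratum has 8,750 per arm and SE0 ≈ 0.00128, so power = Φ[(0.0025 − 0.00251)/0.00128] = 0.496.

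**Step 4: discordance.** With stratum powers a (dense) and b (non-dense), and independent strata: dense-only = a(1−b), non-dense-only = b(1−a), and exactly one = their sum.

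| s | r | a | b | dense-only | non-dense-only | exactly one |
|---|---|---|---|---|---|---|
| 0.5 | 1 | 0.496 | 0.496 | 0.250 | 0.250 | 0.500 |
| 0.5 | 2 | 0.613 | 0.357 | 0.394 | 0.138 | 0.532 |
| 0.4 | 1.5 | 0.495 | 0.496 | 0.249 | 0.251 | 0.500 |
| 0.3 | 1 | 0.326 | 0.635 | 0.119 | 0.428 | 0.547 |
| 0.3 | 2 | 0.464 | 0.526 | 0.220 | 0.282 | 0.502 |

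Over the whole grid, exactly one stratum is significant in 50-55% of trials, dense-only in 12-39% and non-dense-only in 14-43%. Simulation of 200,000 trials per setting agrees.

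**Step 5: other settings.**
- With 12,005 per arm (17,500 × 0.70 asked × 0.98 agreeing, the Oslo figures under Randomization), exactly one stratum is significant in 46-49%.
- With 6.0 to 7.9 per 1000 and 17,500 per arm, it is 44-46%, with dense-only in 12-32%.
- With no true effect, exactly one stratum favours tomo in 2 × 0.025 × 0.975 = 4.9%. Counting either direction it is 2 × 0.05 × 0.95 = 9.5%.

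**Step 6: the alternative.** In the same simulations with a common effect, a Wald interaction test on the log-odds scale signalled a difference in 4.8-4.9% of trials. Its power is low. With no effect in non-dense breasts, it is 23-26% for an odds ratio of 1.42 in dense breasts and 59-65% for 1.84. An odds ratio of about 2.1 is needed for 80%.

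**The case against.** Several stronger readings are tempting, and the protocol does not support them.

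- *Study IV plans only stratum-by-stratum comparisons.* It also plans logistic regression and does not say that the models are fitted separately by stratum. Such a model could carry an interaction term. What can be said is that none is specified.
- *Study IV is purely a question of effect modification.* Its title question concerns women with dense breasts alone. The randomised comparison in that stratum answers it directly, and an interaction term should not displace that estimate.
- *A result significant in dense but not in non-dense breasts will appear by chance about half the time.* The 50-55% counts discordance in either direction. The dense-only pattern is 12-39%, and the reverse is more common when dense women are 30% of participants.
- *The problem arises whatever the truth.* It needs a real common effect. It also cannot be carried over to recall, which was not simulated and where the protocol expects little influence.
- *Density is cut into strata that waste information.* No cut-points are stated, so this is open. A continuous term assumes a log-linear trend and could miss a threshold.

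It is also fair to say that no significance rule is stated for Study IV, so the harm is a foreseeable misreading and not a planned one. A common odds ratio with different baseline rates also gives different absolute gains, so the log-odds scale is not the only relevant one.

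What remains is that the protocol poses a between-density question and names no estimate that answers it.

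**Conclusion.** The point holds in this limited form: the question of how the tomo-versus-DM measures vary with density has no specified interaction or heterogeneity estimate. If readers compared stratum verdicts instead, a common true effect of the design size would produce discordant strata for cancer detection in about half of trials, against about 5% false signals from an interaction test. These sizes rest on two strata, the assumed density shares and detection ratios, and a real common effect.

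The title question needs no new method, only a different label. Sensitivity requires interval cancers, and Table 2 schedules their analysis after paper IV. What Study IV can report is the detection rate.

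This should be changed, but it concerns one secondary paper and does not affect the main comparison.

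**What to change.** 1. For the question of how results vary with density, add a technology-by-density term to the planned logistic regression in all randomised women, for recall and for screen-detected cancer. Use Volpara density as a continuous term or in categories fixed in advance.
2. Report the ratio of odds ratios with its 95% CI. Show stratum-specific rates and rate differences as description, and base no claim that the effect differs by density on a comparison of stratum p-values.
3. Keep the tomo-versus-DM estimate with its CI among women with dense breasts as the answer to the title question, and call the outcome detection rate, not sensitivity.

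The protocol says the Volpara data are available, so the cost is analysis wording only. The drawback is low power: the result may well be no clear difference by density, which is why the estimate and its interval should lead and not the p-value.
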